### 3. PATIENT SELECTION

#### 3.1 Eligibility Criteria

- 3.1.1 Patients must have histologically or cytologically confirmed acute myeloid leukemia (AML).
- 3.1.2 Relapsed or refractory AML without any other reasonable treatment options
- 3.1.3 Age  $\geq$ 18 years.

Because no dosing or adverse event data are currently available on the use of nivolumab in combination with venetoclax and decitabine in patients <18 years of age, children are excluded from this study, but will be eligible for future pediatric trials if combination therapy deemed to warrant further assessment after this pilot study.

- 3.1.4 ECOG performance status  $\leq 2$  (Karnofsky  $\geq 60\%$ , see [Appendix A](#)).
- 3.1.5 Patients must have adequate organ and marrow function as defined below:
  - total bilirubin  $\leq 1.5 \times$  institutional upper limit of normal (ULN),  
(except for patients with Gilbert's disease)
  - AST(SGOT)/ALT(SGPT)  $\leq 5 \times$  institutional ULN
  - glomerular filtration rate (GFR)  $>40$  mL/min/1.73 m^2
- 3.1.6 Human immunodeficiency virus (HIV)-infected patients on effective anti-retroviral therapy with undetectable viral load within 6 months are eligible for this trial.
- 3.1.7 For patients with evidence of chronic hepatitis B virus (HBV) infection, the HBV viral load must be undetectable on suppressive therapy, if indicated.
- 3.1.8 Patients with a history of hepatitis C virus (HCV) infection must have been treated and cured. For patients with HCV infection who are currently on treatment, they are eligible if they have an undetectable HCV viral load.
- 3.1.9 Patients with a prior or concurrent malignancy whose natural history or treatment does not have the potential to interfere with the safety or efficacy assessment of the investigational regimen are eligible for this trial.
- 3.1.10 Patients with known history or current symptoms of cardiac disease, or history of treatment with cardiotoxic agents, should have a clinical risk assessment of cardiac function using the New York Heart Association Functional Classification. To be eligible for this trial, patients should be class 2B or better. A baseline troponin should be within normal limits and baseline oxygen saturation should be greater than or equal to 92%. A baseline ECG should be normal, or with stable changes if patient has chronic ECG changes.
- 3.1.11 Active infection is permitted if the infection is under control.
- 3.1.12 WBC must be  $\leq 25,000$  at time of Day 1 of study treatment. Cytoreduction with Hydrea and leukapheresis is allowed.
- 3.1.13 Risks from venetoclax and nivolumab to the developing human fetus cannot be ruled out. For this reason and because decitabine is known to be teratogenic, women of child-bearing potential and men must agree to use adequate contraception (hormonal or barrier method of birth control; abstinence) prior to study entry and for the duration of study participation. Should a woman become pregnant or suspect she is pregnant while she or her partner is participating in this study, she should inform her treating physician immediately. Contraception use should be continued 6 months after the completion of all study treatments for

women of child bearing potential. Men treated or enrolled on this protocol must also agree to use adequate contraception prior to the study, for the duration of study participation, and 7 months after completion of decitabine, venetoclax, or nivolumab administration.

3.1.14 Ability to understand and the willingness to sign a written informed consent document. Patients with impaired decision-making are allowed to participate as long as the patient has a Legally Authorized Representative (LAR) or caregiver.

### **3.2 Exclusion Criteria**

3.2.1 Patients who have received any prior BCL-2 inhibitor therapy

3.2.2 Patients who have received prior hypomethylating therapy for treatment of AML are excluded

3.2.3 Patients with *known autoimmune disease*. Patients with active autoimmune disease or history of autoimmune disease that might recur, which may affect vital organ function or require immune suppressive treatment including systemic corticosteroids, should be excluded. These include but are not limited to patients with a history of immune related neurologic disease, multiple sclerosis, autoimmune (demyelinating) neuropathy, Guillain-Barre syndrome, myasthenia gravis; systemic autoimmune disease such as SLE, connective tissue diseases, scleroderma, inflammatory bowel disease (IBD), Crohn's, ulcerative colitis, hepatitis; and patients with a history of toxic epidermal necrolysis (TEN), Stevens-Johnson syndrome, or phospholipid syndrome should be excluded because of the risk of recurrence or exacerbation of disease. Patients with vitiligo, endocrine deficiencies including thyroiditis managed with replacement hormones including physiologic corticosteroids are eligible. Patients with rheumatoid arthritis and other arthropathies, Sjögren's syndrome and psoriasis controlled with topical medication and patients with positive serology, such as antinuclear antibodies (ANA), anti-thyroid antibodies should be evaluated for the presence of target organ involvement and potential need for systemic treatment but should otherwise be eligible.

3.2.4 Patients are permitted to enroll if they have vitiligo, type I diabetes mellitus, residual hypothyroidism due to autoimmune condition only requiring hormone replacement, psoriasis not requiring systemic treatment, or conditions not expected to recur in the absence of an external trigger (precipitating event).

3.2.5 Patients should be excluded if they have a condition requiring systemic treatment with either corticosteroids ( $>10$  mg daily prednisone equivalents) or other immunosuppressive medications within 14 days of study drug administration. Inhaled or topical steroids and adrenal replacement doses  $\leq 10$  mg daily prednisone equivalents are permitted in the

absence of active autoimmune disease. Patients are permitted to use topical, ocular, intra-articular, intranasal, and inhalational corticosteroids (with minimal systemic absorption). Physiologic replacement doses of systemic corticosteroids are permitted, even if  $\leq 10$  mg/day prednisone equivalents. A brief course of corticosteroids for prophylaxis (e.g., contrast dye allergy) or for treatment of non-autoimmune conditions (e.g., delayed-type hypersensitivity reaction caused by contact allergen) is permitted.

- 3.2.6 Patients with hyperleukocytosis requiring immediate cytoreductive chemotherapy (WBC  $\geq 100,000$  with symptoms of leukostasis)
- 3.2.7 Isolated extramedullary leukemia of CNS involvement with leukemia
- 3.2.8 Patients who have not recovered from adverse events due to prior anti-cancer therapy (i.e., have residual toxicities  $>$  Grade 1) with the exception of alopecia.
- 3.2.9 Patients who are receiving any other investigational agents.
- 3.2.10 History of allergic reactions attributed to compounds of similar chemical or biologic composition to decitabine, venetoclax, or nivolumab
- 3.2.11 Patients with uncontrolled intercurrent illness.
- 3.2.12 Patients with psychiatric illness/social situations that would limit compliance with study requirements.
- 3.2.13 Pregnant women are excluded from this study because fetal risk has been demonstrated with decitabine with the potential for teratogenic or abortifacient effects. Because there is an unknown but potential risk for adverse events in nursing infants secondary to treatment of the mother with decitabine, breastfeeding should be discontinued if the mother is treated with decitabine. These potential risks may also apply to other agents used in this study.

### **3.3 Inclusion of Women and Minorities**

NIH policy requires that women and members of minority groups and their subpopulations be included in all NIH-supported biomedical and behavioral research projects involving NIH-defined clinical research unless a clear and compelling rationale and justification establishes to the satisfaction of the funding Institute & Center (IC) Director that inclusion is inappropriate with respect to the health of the subjects or the purpose of the research. Exclusion under other circumstances must be designated by the Director, NIH, upon the recommendation of an IC Director based on a compelling rationale and justification. Cost is not an acceptable reason for exclusion except when the study would duplicate data from other sources. Women of childbearing potential should not be routinely excluded from participation in clinical research. Please see <http://grants.nih.gov/grants/funding/phs398/phs398.pdf>.

Planned distribution of subjects

Racial Categories	Ethnic Categories				Total
	Not Hispanic or Latino		Hispanic or Latino		
	Female	Male	Female	Male	
American Indian/ Alaska Native	0	0	0	0	0
Asian	0	0	0	0	0
Native Hawaiian or Other Pacific Islander	0	0	0	0	0
Black or African American	4	4	0	0	8
White	12	16	3	3	34
More Than One Race	0	0	0	0	0
Total	16	20	3	3	42

PHS 398 / PHS 2590 (Rev. 08/12 Approved Through 8/31/2015)

OMB No. 0925-0001/0002

## 4. REGISTRATION PROCEDURES

### 4.1 Investigator and Research Associate Registration with CTEP

Food and Drug Administration (FDA) regulations and National Cancer Institute (NCI) policy require all individuals contributing to NCI-sponsored trials to register and to renew their registration annually. To register, all individuals must obtain a Cancer Therapy Evaluation Program (CTEP) Identity and Access Management (IAM) account at

<https://ctepcore.nci.nih.gov/iam>. In addition, persons with a registration type of Investigator (IVR), Non-Physician Investigator (NPIVR), or Associate Plus (AP) (i.e., clinical site staff requiring write access to Oncology Patient Enrollment Network (OPEN), Rave, or acting as a primary site contact) must complete their annual registration using CTEP's web-based Registration and Credential Repository (RCR) at <https://ctepcore.nci.nih.gov/rcr>.

RCR utilizes five person registration types.

- IVR: MD, DO, or international equivalent,
- NPIVR: advanced practice providers (e.g., NP or PA) or graduate level researchers (e.g., PhD),

- AP: clinical site staff (e.g., RN or CRA) with data entry access to CTSU applications (e.g., Roster Update Management System [RUMS], OPEN, Rave,),
- Associate (A): other clinical site staff involved in the conduct of NCI-sponsored trials, and
- Associate Basic (AB): individuals (e.g., pharmaceutical company employees) with limited access to NCI-supported systems.

RCR requires the following registration documents:

Documentation Required	IV R	NPIVR	AP	A	AB
FDA Form 1572	✓	✓			
Financial Disclosure Form	✓	✓	✓		
NCI Biosketch (education, training, employment, license, and certification)	✓	✓	✓		
GCP training	✓	✓	✓		
Agent Shipment Form (if applicable)	✓				
CV (optional)	✓	✓	✓		

An active CTEP-IAM user account and appropriate RCR registration is required to access all CTEP and Cancer Trials Support Unit (CTSU) websites and applications. In addition, IVRs and NPIVRs must list all clinical practice sites and Institutional Review Boards (IRBs) covering their practice sites on the FDA Form 1572 in RCR to allow the following:

- Addition to a site roster,
- Assign the treating, credit, consenting, or drug shipment (IVR only) tasks in OPEN,
- Act as the site-protocol Principal Investigator (PI) on the IRB approval, and
- Assign the Clinical Investigator (CI) role on the Delegation of Tasks Log (DTL).

In addition, all investigators act as the Site-Protocol PI, consenting/treating/drug shipment, or as the CI on the DTL must be rostered at the enrolling site with a participating organization (i.e., Alliance).

Additional information is located on the CTEP website at <https://ctep.cancer.gov/investigatorResources/default.htm>. For questions, please contact the RCR Help Desk by email at [contact].

## 4.2 Site Registration

This study is supported by the NCI Cancer Trials Support Unit (CTSU).

### IRB Approval

Sites participating with the NCI Central Institutional Review Board (NCI CIRB) must submit the

Study Specific Worksheet for Local Context (SSW) to the CIRB using IRBManager to indicate their intent to open the study locally. The NCI CIRB's approval of the SSW is automatically communicated to the CTSU Regulatory Office, but sites are required to contact the CTSU Regulatory Office at [[contact]](mailto:[contact]) to establish site preferences for applying NCI CIRB approvals across their Signatory Network. Site preferences can be set at the network or protocol level. Questions about establishing site preferences can be addressed to the CTSU Regulatory Office by emailing the email address above or calling [name].

Sites using their local IRB or REB must submit their approval to the CTSU Regulatory Office using the Regulatory Submission Portal located in the Regulatory section of the CTSU website. Acceptable documentation of local IRB/REB approval includes:

- Local IRB documentation,
- IRB-signed CTSU IRB Certification Form, and/or
- Protocol of Human Subjects Assurance Identification/IRB Certification/Declaration of Exemption Form.

In addition, the Site-Protocol PI (i.e., the investigator on the IRB/REB approval) must meet the following five criteria to complete processing of the IRB/REB approval record:

- Holds an Active CTEP status,
- Rostered at the site on the IRB/REB approval (applies to US and Canadian sites only) and on at least one participating roster,
- If using NCI CIRB, rostered on the NCI CIRB Signatory record,
- Includes the IRB number of the IRB providing approval in the Form FDA 1572 in the RCR profile, and
- Holds the appropriate CTEP registration type for the protocol.

## Additional Requirements

Additional requirements to obtain an approved site registration status include:

- An active Federalwide Assurance (FWA) number,
- An active roster affiliation with the Lead Protocol Organization (LPO) or a Participating Organization, and
- Compliance with all protocol-specific requirements (PSRs).

### 4.2.1 Downloading Regulatory Documents

Download the site registration forms from the protocol-specific page located on the CTSU members' website. Permission to view and download this protocol and its supporting documents is restricted based on person and site roster assignment. To participate, the institution and its associated investigators and staff must be associated with the LPO or a Participating Organization on the protocol.

- Log on to the CTSU members' website (<https://www.ctsu.org>) using your CTEP-IAM username and password,
- Click on *Protocols* in the upper left of your screen

- Enter the protocol number in the search field at the top of the protocol tree, or
- Click on the By Lead Organization folder to expand, then select LAO-OH007, and protocol number 10317,
- Click on *Documents*, select *Site Registration*, and download and complete the forms provided. (Note: For sites under the CIRB initiative, IRB data will load automatically to the CTSU as described above.)

#### 4.2.2 Protocol Specific Requirements For 10317 Site Registration

Upon site registration approval in RSS, the enrolling site may access OPEN to complete enrollments. The enrolling site will select their credentialed provider treating the subject in the OPEN credentialing screen, and may need to answer additional questions related to treatment in the eligibility checklist.

- Specimen Tracking System Training Requirement:
  - All data entry users (Clinical Research Associate role) at each participating site will need to complete the Theradex-led training.
  - Theradex will provide a certificate of completion, which will need to be submitted to the CTSU through the Regulatory Submission Portal.
  - The training is a one-time only requirement per individual. If an individual has previously completed the training for another ETCTN study, the training does not need to be completed again nor does the certificate of completion need to be resubmitted to the CTSU. However, new versions of the Specimen Tracking System may require new training.
  - This training will need to be completed before the first patient enrollment at a given site.
  - [name] and [name] are the main points of contact at Theradex for the training ([[contact]](mailto:[contact]) and [[contact]](mailto:[contact]), Theradex [contact]).

#### 4.2.3 Delegation of Tasks Log (DTL)

Each site must complete a protocol-specific DTL using the DTL application in the Delegation Log section on the CTSU members' website. The Clinical Investigator (CI) is required to review and electronically sign the DTL prior to the site receiving an Approved site registration status and enrolling patients to the study. To maintain an approved site registration status the CI must re-sign the DTL at least annually and when a new version of the DTL is released; and activate new task assignments requiring CI sign-off. Any individual at the enrolling site on a participating roster may initiate the site DTL. Once the DTL is submitted for CI approval, only the designated DTL Administrators or the CI may update the DTL. Instructions on completing the DTL are available in the Help Topics button in the DTL application and include a Master Task List, which describes DTL task assignments, CI signature, and CTEP registration requirements.

#### 4.2.4 Submitting Regulatory Documents

Submit required forms and documents to the CTSU Regulatory Office via the Regulatory Submission Portal on the CTSU website.

To access the Regulatory Submission Portal, log on to the CTSU members' website  Regulatory  Regulatory Submission.

Institutions with patients waiting that are unable to use the Regulatory Submission Portal should alert the CTSU Regulatory Office immediately at [name] in order to receive further instruction and support.

#### 4.2.5 Checking Site Registration Status

You can verify your site's registration status on the members' side of the CTSU website.

- Log on to the CTSU members' website
- Click on *Regulatory* at the top of your screen
- Click on *Site Registration*
- Enter your 5-character CTEP Institution Code and click on Go

Note: The status shown only reflects institutional compliance with site registration requirements as outlined above. It does not reflect compliance with protocol requirements for individuals participating on the protocol or the enrolling investigator's status with the NCI or their affiliated networks.

### 4.3 Patient Registration

#### 4.3.1 OPEN / IWRS

The Oncology Patient Enrollment Network (OPEN) is a web-based registration system available on a 24/7 basis. OPEN is integrated with CTSU regulatory and roster data and with the Lead Protocol Organization (LPOs) registration/randomization systems or Theradex Interactive Web Response System (IWRS) for retrieval of patient registration/randomization assignment. OPEN will populate the patient enrollment data in NCI's clinical data management system, Medidata Rave.

Requirements for OPEN access:

- A valid CTEP-IAM account.
- To perform enrollments or request slot reservations: Be on an LPO roster, ETCTN Corresponding roster, or Participating Organization roster with the role of Registrar. Registrars must hold a minimum of an AP registration type.
- If a DTL is required for the study, the registrar(s) must hold the OPEN Registrar task on the DTL for the site.
- Have an approved site registration for a protocol prior to patient enrollment.

To assign an Investigator (IVR) or Non-Physician Investigator (NPIVR) as the treating, crediting, consenting, drug shipment (IVR only), or receiving investigator for a patient transfer in OPEN, the IVR or NPIVR must list the IRB number used on the site's IRB approval on their Form FDA 1572 in RCR. If a DTL is required for the study, the IVR or NPIVR must be assigned the appropriate OPEN-related tasks on the DTL.

Prior to accessing OPEN, site staff should verify the following:

- Patient has met all eligibility criteria within the protocol stated timeframes, and
- All patients have signed an appropriate consent form and HIPAA authorization form (if applicable).

Note: The OPEN system will provide the site with a printable confirmation of registration and treatment information. Please print this confirmation for your records.

Access OPEN at <https://open.ctsu.org> or from the OPEN link on the CTSU members' website. Further instructional information is in the OPEN section of the CTSU website at <https://www.ctsu.org> or <https://open.ctsu.org>. For any additional questions, contact the CTSU Help Desk at [name] or [[contact]](mailto:[contact]).

#### 4.3.2 Special Instructions for Patient Enrollment

This Study will use the ETCTN Specimen Tracking System (STS).

- All biospecimens collected for this trial must be submitted using the ETCTN Specimen Tracking System (STS) unless otherwise noted.
- The system is accessed through special Rave user roles: "CRA Specimen Tracking" for data entry at the treating institutions and "Biorepository" for users receiving the specimens for processing and storage at reference labs and the Biorepository.
- Please refer to the Medidata Account Activation and Study Invitation Acceptance link on the CTSU website under the Rave/DQP tab.
- **Important: Failure to complete required fields in STS may result in a delay in sample processing.** Any case reimbursements associated with sample submissions will not be credited if samples requiring STS submission are not logged into STS.

Detailed instructions can be found in Section 5.3.

#### 4.3.3 OPEN/IWRS Questions?

Further instructional information on OPEN is provided on the OPEN tab of the CTSU website at <https://www.ctsu.org> or at <https://open.ctsu.org>. For any additional questions contact the CTSU Help Desk at [name] or [[contact]](mailto:[contact]).

### 4.4 General Guidelines

Following registration, patients should begin protocol treatment within 10 days. Issues that would cause treatment delays should be discussed with the Principal Investigator. If a patient does not receive protocol therapy following registration, the patient's registration on the study may be canceled. The Study Coordinator should be notified of cancellations as soon as possible.

## 5. BIOMARKER, CORRELATIVE, AND SPECIAL STUDIES

### 5.1 Summary Table for Specimen Collection

Time Point	Specimen	Send Specimens To:
Baseline		
Pre-venetoclax/azole	
 
4 mL Peripheral Blood (EDTA-containing vacutainer) – OATP1B1 plasma biomarker
 
	OSU PharmacoAnalytical Shared Resource for ChOP-KC
	
 
10 mL of bone marrow aspirate in sodium heparin tubes (mandatory)
 
15 mL blood in ACD tubes (mandatory)
 
	Ohio State Leukemia Tissue Bank
	
 
Correlatives: Flow cytometry, Cytogenetics, Next-generation sequencing, Tetramer Analysis, and DNA methylation
 
	
Cycle 1 Day 14 (C1D14)		
Pre-venetoclax, 1h, 2, 4, 7h, 24h	
 
4 mL Peripheral Blood (EDTA-containing vacutainer) – Venetoclax plasma levels, OATP1B1 plasma biomarker assay
 
	OSU PharmacoAnalytical Shared Resource for ChOP-KC
Pre-nivolumab, 4h after end of infusion	
 
3 mL Peripheral Blood (red top vacutainer) – Nivolumab serum levels
 
	
Day 28 +/- 1 day of cycles 1, 2, and 3		
	
 
10 mL of bone marrow aspirate in sodium heparin tubes (mandatory)
 
15 mL blood in ACD tubes (mandatory)
 
	Ohio State Leukemia Tissue Bank
	
 
Correlatives: Flow cytometry, Cytogenetics, Next-generation sequencing, Tetramer Analysis, and DNA methylation
 
	
Day 28 +/- 1 day every 3 cycles starting with cycle 6 (ex. Cycles 6, 9, 12...)		
	
 
10 mL of bone marrow aspirate in sodium heparin tubes (mandatory)
 
15 mL blood in ACD tubes (mandatory)
 
	Ohio State Leukemia Tissue Bank
	
 
Correlatives: Flow cytometry, Cytogenetics, Next-generation sequencing, Tetramer Analysis, and DNA methylation
 
	
Day 28 +/- 1 day of end of every cycle starting with cycle 4 (excluding cycles 6, 9, 12... as above)		
	
 
10 mL blood in ACD tubes (mandatory)
 
	Ohio State Leukemia Tissue Bank
	
 
Correlatives: DNA methylation
 
	
Induction Cycle 2 Day 1		

Pre-nivolumab, 4h after end of infusion	3 mL Peripheral Blood (red top vacutainer) – Nivolumab serum levels	OSU PharmacoAnalytical Shared Resource for ChOP-KC
Maintenance Cycle 1 (Day 1)		
Pre-nivolumab, 4h after end of infusion	3 mL Peripheral Blood (red top vacutainer) – Nivolumab serum levels	OSU PharmacoAnalytical Shared Resource for ChOP-KC
Maintenance Cycle 3 (Day 14)		
Pre-nivolumab, 30 min after end of infusion	3 mL Peripheral Blood (red top vacutainer) – Nivolumab serum levels	OSU PharmacoAnalytical Shared Resource for ChOP-KC
End of Treatment/Relapse		
	

• 10 mL of bone marrow aspirate in sodium heparin tubes (mandatory)

• 15 mL blood in ACD tubes (mandatory)

 

• Correlatives: Flow cytometry, Cytogenetics, Next-generation sequencing, Tetramer Analysis, and DNA methylation

	Ohio State Leukemia Tissue Bank
~ 2 weeks after last nivolumab infusion	

• 3 mL Peripheral Blood (red top vacutainer) – Nivolumab serum levels

	OSU PharmacoAnalytical Shared Resource for ChOP-KC

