#### 2.5.4 Pharmacokinetic (PK) and Pharmacodynamic (PD) studies

While the combination of decitabine and venetoclax has been studied and is currently being utilized clinically, adding nivolumab to this combination is novel. Venetoclax has low bioavailability, high inter-patient PK variability, and is susceptibility to drug-drug interactions (DDIs) through inhibition of intestinal CYP3A4, P-glycoprotein (P-gp), and BCRP and liver CYP3A4 and OATP1B1. Antifungal agents, which are routinely administered concurrently with venetoclax, are moderate-to-strong inhibitors of CYP3A4, and the drug transporters P-gp, BCRP, and OATP1B1. The unpredictable PK properties of venetoclax and high DDI potential warrant detailed plasma PK evaluation of venetoclax during AML therapy.

Plasma biomarker assays for OATP1B1 activity will also be incorporated to determine

OATP1B1 activity in relation to antifungal and venetoclax treatment (DOI: 10.1124/dmd.119.089474). As liver uptake by the transporters OATP1B1 can be a rate-limiting step to CYP3A4-mediated drug metabolism, and azoles and echinocandins are potent inhibitors of OATP1B1, we will also measure plasma biomarkers for OATP1B1 activity before and after administration antifungal/venetoclax. In order to assess the degree of OATP1B1 inhibition, analysis of glycochenodeoxycholate sulfate (GCDGA-S) and chenodeoxycholate-24-glucuronide (CDCA-24G) levels will be performed in plasma samples as validated surrogate endogenous substrates of OATP1B1/OATP1B3. Previous clinical studies have indicated that the AUC of GCDCA-S can be increased >20-fold following treatment with OATP1B1/3 inhibitors, whereas CDCA-24G is only detectable after the administration of OATP1B1/3 inhibitors. In addition to these bile acids, the co-proporphyrins CP-I and CP-III will be examined as OATP1B1/3 biomarkers. These compounds are known OATP1B1/3 substrates in vitro, and their plasma levels are significantly increased in Oatp1a/1b gene cluster knockout mice, compared with wild-type animals (up to 18.4-fold) as well as in humans receiving OATP1B1/3 inhibitors. The selectivity of CP-I and CP-III for OATP1B1 and OATP1B3 has been confirmed by the demonstration that these compounds are not transported by OCT1, OCT2, OAT3, or NTCP.

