Plasma venetoclax and serum nivolumab concentration-time profiles will be analyzed by non compartmental analysis in Phoenix Winonlin, and subsequently by population mixed effects PK modeling using NONMEM. Pharmacokinetic parameters (e.g., Cmax, AUC, CL, V, and t1/2) will be estimated. For venetoclax PK, concurrent antifungal medications will be grouped as strong (e.g., posaconazole, voriconazole) or moderate (e.g., fluconazole, isavuconazole) CYP3A4 inhibitors, or OATP1B1 inhibitors (e.g, micagungin) and included as a covariate in the venetoclax population PK model. Associations between: 1) antifungal drug administered and/or venetoclax exposure and changes in OATP1B1 plasma biomarkers from baseline to post-treatment; and 2) drug exposure parameters such as Cmax and AUC with toxicity or response will be performed using standard t-tests or Wilcoxon rank sum tests and illustrated using boxplots or other graphical displays. Values will be log transformed as appropriate to reflect biologic plausibility assessment.

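### The baseline OATP1B1 sample need only precede venetoclax and azole, although the protocol also calls echinocandins potent OATP1B1 inhibitors, and 9.3 has no rule for patients already on an inhibitor at that draw

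*Combined protocol and SAP*

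**What the plan says.** Section 5.1 asks for one 4 mL blood sample at baseline for the OATP1B1 plasma biomarkers, timed as "Pre-venetoclax/azole". The follow-up samples are at Cycle 1 Day 14: before venetoclax and at 1, 2, 4, 7 and 24 hours. Section 5.4.1.3 sends sites to Appendix F for collection, and Appendix F lists this sample as baseline with no further condition.

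Section 2.5.4 gives the rationale. It states that "azoles and echinocandins are potent inhibitors of OATP1B1" and, in the same sentence, that "we will also measure plasma biomarkers for OATP1B1 activity before and after administration antifungal/venetoclax". It also describes the background use: "Antifungal agents, which are routinely administered concurrently with venetoclax".

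Section 9.3 plans tests (t-test or Wilcoxon rank sum) of the antifungal drug given, venetoclax exposure, or both, against "changes in OATP1B1 plasma biomarkers from baseline to post-treatment". Just before that, it lists antifungal groups for the venetoclax population PK model, one of them being "OATP1B1 inhibitors (e.g, micagungin" (presumably micafungin, an echinocandin).

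Section 3 has no antifungal exclusion or washout. Criterion 3.1.11 reads: "Active infection is permitted if the infection is under control".

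**The concern.** The timing rule in 5.1 protects the baseline against venetoclax and azoles only. A patient already on an echinocandin can give a fully compliant sample that, on the protocol's own pharmacology, is taken while OATP1B1 is inhibited. A patient already on an azole at entry cannot give a compliant sample at all, and nothing says what to do then. Section 9.3 does not separate either kind of patient.

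At stake is the stated purpose in 5.6, which is to assess the effect of antifungals on the OATP1B1 biomarker. A patient on a stable inhibitor at both draws carries little information about that effect in a change score, but still counts as exposed. The result could understate real inhibition, or suggest that one antifungal class inhibits more than another when the only difference is when treatment began. A baseline sample cannot be redrawn once exposure has started.

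**Working it through.** The plan gives no sample size, effect size, SD or power for this analysis, so there is no stated figure to reproduce. The check has two parts.

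**1. The passages side by side**

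| Place | Baseline draw must precede | Echinocandin covered? |
|---|---|---|
| 2.5.4 (intent) | antifungal and venetoclax | yes |
| 5.1 (collection table) | venetoclax and azole | no |
| Appendix F (site instructions) | not stated | no |
| 9.3 (analysis) | no rule on exposure at baseline | no |

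Sites work from 5.1 and Appendix F, so the narrower rule is the one that will be followed. The correlative calendar in 11.1 does not list this sample, so it adds no timing.

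**2. Effect on the change score**

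Inputs, all assumed because the documents do not give them:
- F, the true fold change in a biomarker caused by the inhibitor.
- f, the share of the group already on the inhibitor at the baseline draw.
- For a pre-exposed patient, inhibition is at plateau at baseline, the same drug continues to Cycle 1 Day 14, and venetoclax adds nothing. Such a patient's log change due to the drug is then 0.

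Mean log change in the group = (1−f)·log F + f·0 = (1−f)·log F.

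Observed geometric mean fold change = F^(1−f).

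| True F | f = 0 | f = 0.25 | f = 0.50 | f = 1 |
|---|---|---|---|---|
| 2 | 2.00 | 1.68 | 1.41 | 1.00 |
| 3 | 3.00 | 2.28 | 1.73 | 1.00 |
| 5 | 5.00 | 3.34 | 2.24 | 1.00 |
| 20 | 20.0 | 9.46 | 4.47 | 1.00 |

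The 20-fold row is only an outer illustration. The figure above 20-fold in 2.5.4 is an AUC ratio for GCDCA-S, and the single baseline draw here yields no AUC.

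*Inhibitor versus no antifungal.* With no change in the comparison group, the observed ratio is F^(1−f), which is diluted toward 1.

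*Azole versus echinocandin.* Suppose both classes have the same true F, azole patients have the clean baseline that 5.1 requires, and a share f of echinocandin patients is pre-exposed. The observed ratio is F / F^(1−f) = F^f, against a true ratio of 1. For F = 5:
- f = 0.25: 5^0.25 = 1.50
- f = 0.50: 5^0.50 = 2.24
- f = 1: 5.00

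This contrast moves away from the null.

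*Other patterns.* Under the same model, a patient who stops an echinocandin before Day 14 and whose inhibition has worn off shows a fall toward 1/F. A patient who switches from an echinocandin to an azole of equal strength shows about no change, which dilutes the azole effect.

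**The case against.** The strongest reply is that the protocol does not overlook echinocandins. Section 2.5.4 states an intent to sample before antifungals, so the problem is operational wording that falls short of it. That is correct, and a reader who inferred that the design ignores this class throughout would be going too far.

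Three other stronger readings are also unsupported:

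- *That the antifungal effect is biased to the null in general.* This holds for inhibitor versus no inhibitor. The azole versus echinocandin contrast can be biased the other way. It may well be a main contrast, because 2.5.4 describes antifungal use with venetoclax as routine.
- *That the bias is worst in the group 9.3 labels OATP1B1 inhibitors.* That label is a covariate in the venetoclax population PK model. The biomarker change analysis is a separate sentence and does not use those groups.
- *That many patients will be pre-exposed.* Criterion 3.1.11 does not mention antifungals. Section 6.4.1.1 names only azoles, and it covers venetoclax dosing from ramp-up onward, not drugs taken before the baseline draw. These passages leave pre-exposure possible but do not show how common it is. If 1 of 12 inhibitor patients were pre-exposed, a true 3-fold rise would read 3^(11/12) = 2.7, a small loss.

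It is also fair to say that the plateau assumption is not established in the documents, and that Appendix F refers to a separate PK worksheet, not available here, which might carry more precise timing. Concurrent drugs are recorded, so pre-exposed patients could be identified later.

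What remains is that 5.1, followed exactly, allows an already inhibited baseline, and 9.3 does not say how to handle it. Deciding that after the data are seen would leave the choice of patients open.

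**Conclusion.** The point holds as a mismatch between 2.5.4 and the collection instructions, together with a missing analysis rule in 9.3. Its size depends on f, which the documents do not give. For a true 3-fold change, the reading falls to 2.3 if a quarter of the affected group is pre-exposed and to 1.7 if half is. These figures assume plateau inhibition at baseline, continued treatment to Cycle 1 Day 14 and no added venetoclax effect. The direction depends on the contrast: toward the null for inhibitor versus no inhibitor, and possibly away from it for azole versus echinocandin.

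The consequence is limited. Section 5.6 labels the work exploratory, although it serves the PK/PD secondary objective 1.2.8. It does not bear on the MTD or on the rule of 13 or more responses in 30. The correction is worth making because it is cheap and has to be in place before the baseline samples are drawn.

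**What to change.** - **5.1 and Appendix F:** time the baseline OATP1B1 draw *before venetoclax and, where possible, before any azole or echinocandin*, to match 2.5.4. This concerns the timing of the sample only; antifungal treatment is not changed or delayed for it. Check that the PK worksheet says the same.
- **9.3:** restrict the antifungal change-from-baseline analysis to patients not on an azole or echinocandin at the baseline draw. Report pre-exposed patients separately, using Cycle 1 Day 14 levels instead of change. The wording in 5.1 cannot help a patient who enters already on an inhibitor, so this rule does most of the work.
- **Identification:** use the concurrent medications assessed at screening (Section 11, note a) and captured on the case report form (6.4.1.1). Confirm that the form allows antifungal start dates to be compared with the date of the draw.

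The cost is wording in three places, with no new samples. The downside is fewer patients in the change-from-baseline comparison, in a trial capped at 42. The number set aside should be reported.
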